4.2.2 Ofatumumab Guidelines

Ofatumumab treatment guidelines follow the manufacturer recommendations for 12 ofatumumab infusions administered over 6-7 months: 8 weekly ofatumumab infusions followed by an ofatumumab infusion every month for 4 months. During the 6-7 months of ofatumumab infusions, therapy may be modified due to toxicity as described below. Ofatumumab dosing will not be extended beyond the 12 ofatumumab infusions, as described in [Table 4](#) and the latest ARZERRA[®] prescribing information.^{10, 11}

4.2.2.1 Ofatumumab treatment modification guidelines due to ofatumumab related toxicities

Subjects will be monitored continuously for toxicity while on study treatment. Toxicity will be assessed using the NCI CTCAE Version 4.03. If a subject has an AE at least possibly related to ofatumumab, then dose interruptions/holds with possible modifications are described below. If the dose of ofatumumab is reduced, all reductions should be made per Prescribing Information.^{10, 11} Additional details on study drug dosage and administration are described in [Section 7.2.1](#) and [7.2.2](#), respectively. Deviations from these guidelines may occur based on the clinical judgment of the Investigator with notification to the Medical Monitor/Sponsor. There should be no attempt to make up for a missed weekly dose of ofatumumab or a monthly dose of ofatumumab if delayed by >3 weeks.

Table 10: Dose Interruption/Hold/Modifications for Ofatumumab-Related Toxicities

Ofatumumab-related Toxicities ^{a, b}	Dose Interruption/Hold/Modification/Recommendation for Ofatumumab
Infusion Reactions	Infusion interruptions 
 • For Grade 1, 2, or 3 infusion reaction, if the infusion reaction resolves or remains less than or equal to Grade 2, resume infusion with the following modifications according to the initial Grade of the infusion reaction. 
 ○ Grade 1 or 2: Infuse at one-half of the previous infusion rate. ○ Grade 3: Infuse at a rate of 12 mL/hour. • After resuming the infusion, the infusion rate may be increased according to the Principal Investigator, based on subject tolerance. • For Grade 4 infusion reactions, do not resume the infusion. 
Modifications:
 
 • Grade 3 or 4 infusion reaction with previous infusion: 
 ○ Reduce next ofatumumab dose to 300 mg • Increase subsequent dose(s) to 2000 mg if no Grade 3 or 4 infusion reaction occurs
Nonhematologic: Grade 3 or higher	Withhold until return to ≤ Grade 1 or baseline level; re-challenge therapy at original dose level.
Hematologic: Grade 3 or higher febrile neutropenia	Withhold until return to ≤ Grade 1 or baseline level; re-challenge therapy at original dose level.
Grade 3 or higher thrombocytopenia associated with Grade 2 or higher hemorrhage	Withhold until return to ≤ Grade 1 or baseline level; re-challenge therapy at original dose level.

- a. Related = possible, probable, or definite relationship to ofatumumab as defined in [Section 8.2.1](#).
- b. Toxicity grades are defined per CTCAE Version 4.03. Note if parameter is not defined by CTCAE, then AE grading criteria ([Section 8.2.1](#)) should be utilized.

Treatment Interruption for Infusion-related Toxicity

The initial dose of ofatumumab will be 300 mg IV to reduce the possibility of infusion reactions. If the subject tolerates this infusion without occurrence of any infusion-associated AEs of ≥ Grade 3, subsequent doses of ofatumumab will be at a dose of 2000 mg for the duration of study treatment. If the subject experiences Grade 4 infusion reaction, the infusion should be stopped. If the subject experiences a Grade 1-3 infusion reaction during the first infusion, ofatumumab should be interrupted and appropriate supportive care given. If the infusion reaction improves to ≤ Grade 2, then administer at a slower rate (as described in [Table 10](#) and the ARZERRA[®] package insert).

Appropriate supportive care should also be given, until the infusion reaction improves to ≤ Grade 1. Following a Grade 3/4 infusion reaction, the next ofatumumab dose should be given at the starting dose of 300 mg. The ofatumumab dose may be escalated to 2000 mg following a dose in which no Grade 3/4 infusion reactions are experienced.

Treatment Interruption for Nonhematologic Toxicity

Treatment with ofatumumab may be interrupted at any time, at the discretion of the treating physician. Treatment with ofatumumab should be interrupted for the following nonhematologic toxicities:

- Any Grade 3 or higher nonhematologic toxicity (with the following modifications)
 - Grade 3 or higher diarrhea despite optimal antidiarrheal treatment
 - Grade 3 nausea, or vomiting despite optimal anti-emetic treatment
 - Grade 3 or higher cardiac events including \geq Grade 3 QTcF prolongation (≥ 500 ms). A \geq Grade 3 QTcF prolongation requires triplicate ECGs with the average measurement used and the use of Fridericia's correction method (QTcF). For subjects with a right or left BBB, a Grade 3 QTc prolongation is defined as an increase in QTcF of >100 ms from the pre-dose ECG to any post dose ECG as the QRS interval is prolonged at Baseline (by approximately 40 ms) in subjects with a BBB
 - Subjects who develop infections requiring IV antibiotics will have treatment held until the infection resolves (subject may restart ofatumumab while completing a course of oral therapy). Requirement of prophylaxis for further infection will not prevent the subject from continuing treatment

Subjects requiring dose interruption should be re-evaluated at least weekly until the toxicity improves to \leq Grade 1 or returns to Baseline level.

Treatment Interruption for Hematologic Toxicity

Worsening or transient Grade 3 or higher neutropenia, anemia, and/or thrombocytopenia caused by the subject's existing disease (CLL/SLL) or by ofatumumab are to be expected. Blood counts should be monitored as prescribed in the protocol with the frequency increased as clinically indicated in the setting of new or worsening Grade 3 or higher cytopenias.

Ofatumumab dosing may be interrupted at any time, at the discretion of the treating physician. Treatment with ofatumumab should be held for the following symptomatic hematologic toxicity:

- Grade 3 or higher febrile neutropenia
- Grade 3 or higher thrombocytopenia associated with Grade 2 or higher hemorrhage

The subject should be re-evaluated at least weekly until the toxicity improves to \leq Grade 1 or returns to Baseline.

Ofatumumab will be discontinued in subjects who develop viral hepatitis or have a diagnosis or symptoms suspicious of progressive multifocal leukoencephalopathy (PML).

4.3 TREATMENT DISCONTINUATION

A subject should be withdrawn from the study treatment if, in the opinion of the investigator, it is medically necessary, or if it is the wish of the subject.

Subjects will be withdrawn from treatment in case of any of the following reasons:

- An adverse event that requires permanent discontinuation of duvelisib or ofatumumab
- Protocol-specified disease progression
- Subject death
- Subject lost to follow-up
- Noncompliance to protocol
- Investigator decision (including for benefit as described in [Section 4.2.1.2](#))
- Subject becomes pregnant
- Termination of the study by sponsor
- Voluntary withdrawal by subject
- Subject requires additional anticancer therapy

Adverse events leading to the discontinuation of a subject will be followed until resolution, resolution to baseline or until the event is considered stable or chronic.

If a subject does not complete dosing through Cycle 19 Day 1 (duvelisib) or through Cycle 7 (ofatumumab), then he/she should attend an Early Treatment Termination (ETT) Visit within 7 days of last dose or the decision leading to treatment discontinuation (see [Section 6.4](#)). Assessments collected within 14 days of the ETT (within 30 days for Disease Response Assessment and QoLs) Visit do not need to be repeated at the ETT Visit. Following last dose, either due to ETT or completion of dosing, all subjects will complete a 30-day safety follow-up visit (see [Section 6.5.1](#)). Scans will be performed at the ETT if a previous scan has not been performed within 30 days of the ETT visit. All subjects who discontinue treatment will be followed for survival (see [Section 6.5.3.2](#)).

Subjects who discontinue study treatment for reasons other than PD, and have not withdrawn consent from overall study participation should enter the Clinical Assessment Period ([Section 6.5.2](#)) and continue Disease Response Assessments ([Section 6.5.3.1](#)) as applicable.

4.4 STUDY DISCONTINUATION

Subjects may voluntarily withdraw from the study at any time for any reason without prejudice.

Subjects will be withdrawn from the study in case of any of the following reasons:

- Subject death
- Subject lost to follow-up
- Completion of the follow-up period
- Termination of the study by sponsor
- Voluntary withdrawal by subject

If the subject withdraws consent from the study overall participation (and not just study treatment), no further evaluations should be performed and no attempts should be made to collect additional data.

5 STUDY POPULATION

Approximately 300 subjects with a diagnosis of relapsed and/or refractory CLL or SLL will enroll in the study and be randomized equally (150 subjects per arm) to one of two treatment groups (25 mg duvelisib BID or ofatumumab).

Approximately 100 sites will be initiated worldwide. It is anticipated that the entire study will accrue subjects over approximately 16 months from the randomization of the first subject.

5.1 ENTRY CRITERIA

5.1.1 Inclusion Criteria

Subjects must meet all of the following criteria:

1. ≥ 18 years of age
2. Diagnosis of active CLL or SLL that meets at least one of the IWCLL 2008 criteria for requiring treatment (Binet Stage \geq B and/or Rai Stage \geq I)
3. Disease that has progressed during or relapsed after at least one previous CLL/SLL therapy
4. Not appropriate for treatment with a purine-based analogue regimen (per NCCN or European Society for Medical Oncology [ESMO] guidelines), including relapse \leq 36 months from a purine-based chemoimmunotherapy regimen or relapse \leq 24 months from a purine-based monotherapy regimen
5. A cytogenetics or FISH analysis of the leukemic cells within 24 months of randomization is required to document the presence or absence of del(17p). Note: if a sample from within 24 months is not available, it should be evaluated as part of the screening laboratory evaluation to inform stratification
6. Measurable disease with a lymph node or tumor mass > 1.5 cm in at least one dimension as assessed by computed tomography (CT)
7. Eastern Cooperative Oncology Group (ECOG) performance status of 0 to 2 (corresponds to Karnofsky Performance Status [KPS] \geq 60%)
8. Willingness by subject to be randomized to receive either ofatumumab or duvelisib at the dose and schedule defined in the protocol
9. Must meet the following laboratory parameters:
 - Serum aspartate transaminase (AST/SGOT) or alanine transaminase (ALT/SGPT) ≤ 3 x upper limit of normal (ULN)
 - Total bilirubin ≤ 1.5 x ULN
 - Serum creatinine ≤ 2.0 x ULN
 - Hemoglobin ≥ 8.0 g/dL with or without transfusion support
 - Platelet count $\geq 10,000$ μ L with or without transfusion support

10. For women of childbearing potential (WCBP): negative serum β -human chorionic gonadotropin (β hCG) pregnancy test within 1 week before randomization (WCBP defined as a sexually mature woman who has not undergone surgical sterilization or who has not been naturally post-menopausal for at least 24 consecutive months [women \leq 55 years] or 12 consecutive months [women $>$ 55 years])
11. Willingness of male and female subjects who are not surgically sterile or postmenopausal to use medically acceptable methods of birth control from the first dose of study drug to 30 days after the last dose of duvelisib and for 12 months after last dose of ofatumumab. Sexually active men, and women using oral contraceptive pills, should also use barrier contraception
12. Ability to voluntarily sign consent for and adhere to the entire study visit schedule and all protocol requirements
13. Signed and dated institutional review board (IRB)/independent ethics committee (IEC)-approved informed consent form (ICF) before any study specific screening procedures are performed

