6.3.6 Concomitant Medication and Therapies

At every clinic visit, assessment of concomitant medications and procedures will occur. At screening, concomitant / previous medications will be assessed and includes all medications/procedures that have occurred within the previous 30 days.

For all subjects during treatment

- *Antimicrobial prophylaxis:*

Infection is a recognized complication in patients with relapsed/refractory CLL leading to many treatment centers to employ antimicrobial prophylaxis. Based on the duvelisib clinical experience to date and the ofatumumab product label (ARZERRA[®]) the following are required or recommended:

- Pneumocystis infections have been reported in clinical studies with duvelisib and ofatumumab, therefore subjects are required to receive pneumocystis prophylaxis concomitant with treatment with study drug. Please follow institutional guidelines. Subjects who are found to be intolerant of pneumocystis prophylaxis may continue with study treatment at the discretion of the Investigator.
- Herpes simplex (HSV) and herpes zoster (VZV) infections have been observed with duvelisib and ofatumumab; therefore, subjects are recommended to receive herpes (HSV/VZV) prophylaxis concomitant treatment per investigator discretion. Please follow institutional guidelines.
- For subjects with history of CMV infection that required treatment, prophylactic treatment per institutional guidelines is recommended.
 - Subjects with history of CMV or EBV infection and/or who enter the study while receiving antiviral prophylaxis should be monitored for reactivation via serology or viral load detection per institutional guidelines while on study treatment
- Other antimicrobial prophylaxis based on the individual subject's medical history may be considered if no contraindications based on drug-drug interactions (DDI). See below.

- *Transfusion support (prophylaxis or supportive care):*

At study entry or during any time on treatment, blood cell transfusions (packed red blood cells or platelets) to maintain a subject's hemoglobin ≥ 8.0 mg/dL or platelets $\geq 10,000$ per μL is recommended. Transfusions may be used at any time as clinically indicated.

For subjects treated with ofatumumab

- *Premedication:*

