6.3.9.2 Investigator assessment of response and progression status

Assessment of response and progression status will be evaluated by the investigator for clinical decision-making using criteria derived from the IWCLL response criteria for subjects with CLL ([Table 11](#)) and IWG response criteria for subjects with SLL ([Table 12](#)).

The CLL/SLL response definitions for this protocol (provided below) include modifications to the IWCLL/IWG response criteria related to PD based on the understanding that agents like duvelisib, which target the B-cell receptor signaling pathway, can mobilize CLL/SLL cells from tissues into the peripheral blood²³ interfering with their homing.^{24,25} Specifically, two modifications have been made: (1) an additional category has been added to allow for PR with lymphocytosis (PRwL); and (2) the criteria for PD do not include PD based only on worsening lymphocytosis or isolated increase in target lesion(s) in the absence of other objective evidence of disease progression.

Table 11: CLL Response Criteria (modified from IWCLL) ^{1, 22}

Variable	Complete Response (CR)	Partial Response (PR)	Progressive Disease (PD)
GROUP A			
Lymphadenopathy (CT scan)	None > 1.5 cm	Decrease \geq 50%	New lesions (> 1.5 cm) or increase \geq 50% in diameter of any single lesion or the SPD ^a
Hepatomegaly (CT scan) ^b	None	Decrease \geq 50% or normal	Increase \geq 50% of previously noted or de novo appearance ^a
Splenomegaly (CT scan) ^b	None	Decrease \geq 50% or normal	Increase \geq 50% of previously noted or de novo appearance ^a
Blood lymphocytes	< 4000/ μ L	Decrease \geq 50% from baseline or < 4,000/ μ L	Increase \geq 50% over baseline or nadir (whichever is lowest) and \geq 5,000 per μ L
Marrow ^c	Normocellular, < 30% lymphocytes, no B-lymphoid nodules. Hypocellular defines CRi in CLL subjects only	If performed: 50% reduction in marrow infiltrate, or presence of B-lymphoid nodules	
GROUP B			
Platelet count without transfusions or growth factors	> 100,000/ μ L	> 100,000/ μ L or increase \geq 50% over baseline	Decrease of \geq 50% from baseline secondary to CLL
Hemoglobin without transfusions or growth factors	> 11.0 g/dL	> 11.0 g/dL or increase \geq 50% over baseline	Decrease of > 2 g/dL from baseline secondary to CLL
Neutrophils without growth factors	> 1500/ μ L	> 1500/ μ L or \geq 50% improvement over baseline	

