## 6.8 Baseline Values

Unless otherwise specified, the baseline value is defined as the value collected at the time closest to, and prior to, the start of study drug administration. Values collected at unscheduled visits prior to the start of the study drug administration will be included in the calculation of baseline values.

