#### 7.2.2.4 *Hematologic Improvement Rate*

A subject with a hematologic improvement is one who consistently met the criteria of an improvement in neutrophil count, hemoglobin or platelet count for a period of at least 60 days during which the subject did not have a transfusion or exogenous cytokines. Missing data or missing scheduled assessments during a potential 60-day hematologic improvement episode will result in categorization of not having a hematologic improvement.

The number of subjects with hematologic improvement, estimated hematologic improvement rate, and a 2-sided 95% CI will be provided for each treatment arm.

Hematologic improvement rate will be compared between treatment groups using one-sided CMH test. The strata for the test will be those used for stratified randomization, with potential pooling of strata specified earlier in [Section 7.2](#).

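### Baseline blood counts may be transfusion-supported while hematologic improvement and Table 11 Group B score later values without support; the SAP needs a support-free baseline for these criteria

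*Protocol*

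**What the plan says.** - **Entry.** Protocol Section 5.1.1, criterion 9, sets the hemoglobin floor at "8.0 g/dL with or without transfusion support". The platelet floor of 10,000/µL carries the same allowance.
- **Transfusion.** Section 6.3.6 recommends transfusion to hold those two levels; its sentence begins "At study entry or during any time on treatment, blood cell transfusions (packed red blood cells or platelets". Section 6.3.6.8 also lets a stable dose of erythropoietin for baseline anemia continue.
- **Baseline.** SAP V4.0 Section 6.8 states that, unless specified otherwise, "the baseline value is defined as the value collected at the time closest to, and prior to, the start of study drug administration". It sets no transfusion-free or growth-factor-free interval.
- **Hematologic improvement.** Protocol Section 3.2 accepts any one of three lineages, held for at least 60 days: neutrophils above 1,500/µL, hemoglobin above 11 g/dL or platelets above 100,000/µL, or in each case a rise of at least 50% from baseline. SAP Section 7.2.2.4 limits this to a period "during which the subject did not have a transfusion or exogenous cytokines". That condition covers the improvement episode, not the baseline.
- **Table 11 (CLL), Group B.** The rows are labelled "Hemoglobin without transfusions or growth factors" and "Platelet count without transfusions or growth factors". The response limbs use the same absolute or +50% thresholds. The hemoglobin progression limb is "Decrease of > 2 g/dL from baseline secondary to CLL"; the platelet limb is a fall of at least 50% with the same attribution. One Group B criterion can be enough for progression, and a partial response needs one alongside Group A.
- **Independent review.** Section 6.3.9.3 has the panel use blood data as well as imaging.
- **Table 12 (SLL).** It has no hemoglobin or platelet limb.

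**The concern.** A change from baseline is interpretable only if both measurements are taken under the same conditions. Here the later value must be unsupported, but the baseline may have been raised by transfusion or a growth factor. The difference then mixes the change in disease with the support that was removed.

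Two misclassifications are possible. A subject whose own count has risen by half or more can be recorded as not improved, because the comparison is with an inflated starting value. And a subject with unchanged disease can show a fall from that value. The first affects the hematologic improvement rate, and the Group B part of response in CLL if the independent review uses the same baseline. The second could reach PFS in CLL, under the same condition.

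**Working it through.** **Design figure.** Inputs from Protocol Section 9.1: 185 events, hazard ratio 0.6, 1:1 allocation, one-sided 0.025.
Power = Φ(√185/2 × |ln 0.6| − 1.960) = Φ(6.801 × 0.5108 − 1.960) = Φ(1.514) = 93.5%. Simulating the two-look design with the stated bounds 0.0015 and 0.0245 gives 93.4%. The stated 93% reproduces.

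**When a true improvement is hidden.** Let u be the unsupported starting level, B the recorded supported baseline (B > u), f the later unsupported value and T the absolute threshold. The improvement is lost in that lineage when 1.5u ≤ f < 1.5B and f ≤ T. This requires 1.5u ≤ T, so the relative limb can decide only up to u = T/1.5:
- Platelets: 100,000/1.5 = 66,667/µL.
- Hemoglobin: 11/1.5 = 7.33 g/dL.
- Neutrophils (growth factors only): 1,500/1.5 = 1,000/µL.

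For hemoglobin, a recorded baseline at the entry floor gives 1.5 × 8.0 = 12.0, above 11, so the +50% limb adds nothing at B ≥ 8.0. Only subjects with u below about 7.3 can lose an improvement.

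**When lost support alone meets a Group B fall.** With no change in disease, f = u. The hemoglobin limb is met if B − u > 2 g/dL. The platelet limb is met if (B − u)/B ≥ 0.5, that is, if support at least doubled the count.

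**Illustrations (assumed patients, not data):**

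| Case | B | u | f | Against B | Against u |
|---|---|---|---|---|---|
| Platelets, hidden rise | 30,000 | 12,000 | 24,000 | −20%, not met | +100%, met |
| Hemoglobin, hidden rise | 9.0 | 6.5 | 10.0 | +11%, not met | +54%, met |
| Platelets, apparent fall | 30,000 | 14,000 | 14,000 | −53%, limb met | 0% |
| Hemoglobin, apparent fall | 10.5 | 8.0 | 8.0 | −2.5 g/dL, limb met | 0 |

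The hidden rises count as missed only if the subject's other lineages also fail.

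**Scale for PFS (pure assumption).** If a share q of the 185 events were artefacts with hazard ratio 1, then ln HR = (1 − q) ln 0.6:

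| q | HR | Power |
|---|---|---|
| 0% | 0.600 | 93.5% |
| 2% | 0.606 | 92.6% |
| 5% | 0.616 | 91.0% |
| 10% | 0.631 | 87.8% |

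Nothing in the documents supports any particular q. The table shows direction and scale only.

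**The case against.** The strongest reply concerns the primary endpoint, and most of it stands.

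- The Table 11 row label can be read as defining the variable at both times, so that baseline is also unsupported. No passage shows that SAP Section 6.8 binds the independent review, whose responses enter the SAP as inputs.
- The Group B limbs require attribution to CLL. The PFS rules (Protocol Table 13, SAP Appendix A) date an event only at a finding of unequivocal progression. A panel weighs all the data. The CT note under Table 11 mentions worsening cytopenias and arguably asks for imaging there too.
- On-treatment transfusion is recommended below 8.0 g/dL or 10,000/µL. A subject who needed support at entry would often keep receiving it, and supported values cannot be scored. Unsupported values below those levels should be uncommon.
- SLL is unaffected, since Table 12 has no such limb.

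These safeguards are incomplete. Attribution to CLL does not separate worsening from lost support, because the unsupported cytopenia may itself be due to CLL. The alternative reading of the row label is not written down.

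For hematologic improvement the reply is weaker. The SAP does not base that endpoint on independent review, Section 6.8 applies, and nothing in Section 7.2.2.4 overrides it. What does stand is that any one lineage suffices, that the absolute thresholds do not depend on baseline, and that SAP V4.0 Section 6.3 keeps this endpoint out of formal testing, although Protocol Section 9.4.2 still lists it as key secondary.

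**Conclusion.** The gap is real and narrow. As written, the hematologic improvement rule can misclassify subjects with a supported baseline, mainly through platelets. The Group B response limbs in CLL share the problem if the independent review uses the same baseline. The progression route is conditional in the same way and is limited by attribution, the unequivocal-progression requirement and panel review.

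A reader might infer that unchanged disease will be counted as progression in the primary endpoint, with a measurable loss of power. The documents do not support that: they do not tie the review panel to SAP Section 6.8, and they give no share of supported baselines. If artefactual events were unrelated to treatment, they would pull the hazard ratio toward 1 and would not create false superiority.

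A reader might also infer that the +50% hemoglobin limb can never operate. That too goes beyond the text. Screening may precede dosing by up to 30 days, so the last pre-dose hemoglobin can lie below the 8.0 g/dL entry floor, and transfusion is recommended, not required.

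The number of subjects affected, and the effect on the hazard ratio and power, are unknown.

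**What to change.** 1. **SAP Sections 6.8 and 7.2.2.4.** For these criteria, define baseline hemoglobin, platelets and neutrophils as the last pre-dose value free of the relevant transfusion or growth factor for a pre-specified interval. Failing that, use the pre-transfusion screening value.
2. **Table 11 and the instructions to the independent review.** State that the restriction on transfusions and growth factors applies to baseline as well as to follow-up.
3. **No clean baseline: improvement and response.** Use only the absolute thresholds for that lineage (hemoglobin above 11 g/dL, platelets above 100,000/µL, neutrophils above 1,500/µL).
4. **No clean baseline: progression.** Table 11 has no absolute Group B threshold for progression, so the fallback in step 3 would remove the limb and could miss real progression. Keep the limb in the primary analysis, flag the subject, and add a PFS sensitivity analysis that does not count progression based on a Group B fall alone in flagged subjects.

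**Cost.** Wording in the SAP, Table 11 and the review instructions, plus a derivation from records already collected: Protocol Section 6.3.6 covers medications and procedures for the 30 days before screening and at every visit. A few subjects lose the relative limb for one lineage. A pre-transfusion value may be a low reading, which would slightly favour apparent improvement in both arms. No entry or transfusion rule changes.
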